5.8 Acute GvHD

Any patient with new rash, diarrhea or elevated liver enzymes should be evaluated for presence of acute GvHD. In the event a study participant were to develop acute GvHD grade III-IV after initiating belimumab therapy, belimumab treatment will be held. Belimumab administration can be delayed for up to two weeks, however, if the grade of acute GvHD does not improve to grade II or less by that time, belimumab will be discontinued indefinitely and patient will be taken off study.

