5.4 Duration of Therapy

Treatment may continue for six months, or until one of the following criteria applies:

- Documented and confirmed original hematologic disease relapse
- Death
- Adverse event(s) that, in the judgment of the investigator, may cause severe or permanent harm or which rule out continuation of study drug
- General or specific changes in the patient's condition render the patient unable to receive further treatment in the judgment of the investigator
- Grade III-IV acute GvHD not responding to therapy after 2 weeks
- Serious noncompliance with the study protocol
- Lost to follow-up
- Patient withdraws consent
- Investigator removes the patient from study
- The Siteman Cancer Center decides to close the study

If at any time the constraints of this protocol are considered to be detrimental to the patient's health and/or the patient no longer wishes to continue protocol therapy, the protocol therapy should be discontinued and the reason(s) for discontinuation documented in the case report forms. Subjects who prematurely discontinue treatment for any reason will be followed as indicated in the study calendar.

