5.5 Duration of Follow-up

Subjects will be followed after discontinuation of treatment every 3 months during the first 2 years post-C1D1 and then annually for 5 years post-C1D1 or until death, whichever occurs first. Subjects removed from study for unacceptable adverse events will be followed until resolution or stabilization of the adverse event.

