8.2 Secondary Endpoints

Subjects who receive at least 2 cycles of belimumab are evaluable for secondary and explorative endpoints.

1. Incidence and severity of chronic GvHD at 6, 12 and 24 months after alloHCT

The presence of chronic GvHD will be determined according to the 2014 NIH Criteria (**Appendix B**). If chronic GvHD is diagnosed, each organ will be scored 0-3 and graded, according to the 2014 NIH criteria for Diagnosing and Staging of Chronic GvHD (**Appendix D**). These data will allow calculation of the NIH global severity score of mild, moderate or severe (**Appendix E**). Data will be collected on forms capturing chronic GvHD diagnosis and activity according to the 2014 NIH Criteria for chronic GvHD.

2. Incidence and severity of acute GvHD at 3 and 6 months after alloHCT

Acute GvHD will be graded according to modified Minnesota CIBMTR (**Appendix F**).

3. Overall survival at 6, 12 and 24 months after alloHCT

Overall survival will be determined from date of belimumab initiation, with death from any cause as the event of interest, and censoring at last follow up date for those with incomplete observations.

4. Relapse rate at 6, 12 and 24 months after alloHCT

Relapse rate will be determined from date of belimumab initiation and censoring at last follow up date for those with incomplete observations.

5. Overall corticosteroid requirement (dose and duration) for treatment of chronic GvHD at 6, 12 and 24 months after alloHCT

The dose of corticosteroids will be captured at each study visit.

6. Use of alternative treatment modalities for chronic GvHD at 6, 12 and 24 months after alloHCT

The use of additional systemic immune suppressive agents will be captured at each study visit.

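### Section 5.8 takes patients with unresolved grade III-IV acute GvHD off study, while Sections 5.4 and 5.5 keep them in follow-up; read literally, 5.8 makes censoring of survival and relapse depend on prognosis

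*Combined protocol and SAP*

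**What the plan says.** Three sections of the protocol deal with the same patient.

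- **Section 5.8 (Acute GvHD).** Belimumab is held for grade III-IV acute GvHD. If the grade has not come down to II or lower within two weeks, "belimumab will be discontinued indefinitely and patient will be taken off study". Stopping the drug and leaving the study are named as two actions.
- **Section 5.4 (Duration of Therapy).** Among the reasons to end treatment is "Grade III-IV acute GvHD not responding to therapy after 2 weeks". The section closes with: "Subjects who prematurely discontinue treatment for any reason will be followed as indicated in the study calendar".
- **Section 5.5 (Duration of Follow-up).** "Subjects will be followed after discontinuation of treatment every 3 months during the first 2 years post-C1D1", then yearly to 5 years or until death. A second sentence adds: "Subjects removed from study for unacceptable adverse events will be followed until resolution or stabilization of the adverse event".

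Section 8.2 defines overall survival from the start of belimumab, "with death from any cause as the event of interest, and censoring at last follow up date for those with incomplete observations". For relapse it says: "Relapse rate will be determined from date of belimumab initiation and censoring at last follow up date for those with incomplete observations". It states no censoring rule for chronic GvHD, corticosteroid requirement or alternative treatments, and no handling of patients whom the protocol itself removes. Section 13 plans descriptive analyses of 10 patients with a 90% exact binomial interval for preliminary efficacy, no hypothesis test, and use of the data for phase II sample-size estimates.

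**The concern.** A site reading 5.8 could end all follow-up for a patient at the point where that patient is doing badly. A site reading 5.4 would keep the same patient to 24 months and beyond. Under the first reading, survival and relapse are censored because of severe acute GvHD that has not improved. Standard censored-data estimates assume that patients who leave have the same outlook as those who stay, and that is hard to defend here.

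Two other parts of the plan make continued follow-up matter more. Sections 8.3 and 13 compare the cohort with institutional controls (about 100 banked subjects) whose outcomes come from a database, and nothing in the plan truncates a control's outcomes for unresolved acute GvHD. Follow-up could therefore differ between the groups. Section 5.10 suspends the study for a possibly related death that occurs during participation, and it is unclear whether a death after removal under 5.8 would count.

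**Working it through.** **1. Plan's own figures.** The plan gives no figure on this point. Its two stated operating characteristics concern serious adverse events in 10 patients. They reproduce and are unaffected: 1 − 0.8^10 = 89.3% (stated 90%), and 1 − 0.95^10 − 10 × 0.05 × 0.95^9 = 8.6% (stated as less than 10%).

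**2. How often the rule might bite.** The documents give no rate of unresolved grade III-IV acute GvHD, so a range is assumed. The chance that at least one of 10 patients is affected is 1 − (1 − p)^10:

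| Assumed p per patient | Chance of at least one |
|---|---|
| 5% | 40% |
| 10% | 65% |
| 20% | 89% |

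**3. Effect on survival.** Assumptions: 10 patients, all with at least 2 cycles (the Section 8.2 evaluability rule); k removed and censored before any other death; one later death among the rest; a Kaplan-Meier estimate, which the plan does not name. With censoring, S = 1 − 1/(10 − k). With full follow-up, S = 1 − (1 + m)/10, where m of the k removed patients die.

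| Removed (k) | Die among removed (m) | With censoring | Full follow-up | Difference (points) |
|---|---|---|---|---|
| 1 | 1 | 8/9 = 88.9% | 80% | +8.9 |
| 1 | 0 | 88.9% | 90% | −1.1 |
| 2 | 2 | 7/8 = 87.5% | 70% | +17.5 |
| 2 | 1 | 87.5% | 80% | +7.5 |
| 2 | 0 | 87.5% | 90% | −2.5 |

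With one removed and two other deaths, the censored estimate is (8/9)(7/8) = 77.8%, against 70% if the removed patient dies and 80% if not.

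The direction turns on whether removed patients die more often than those who remain. For k = 2, if q is the proportion of removed patients who die, the difference is 0.875 − (9 − 2q)/10 = 0.2q − 0.025. This is zero at q = 1/8, the death proportion among the other eight.

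**4. Chronic GvHD.** Assume two removed and three cases among the other eight (90% exact intervals):

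- removed patients dropped from the denominator: 3/8 = 37.5% (11.1% to 71.1%);
- removed patients counted as non-cases: 3/10 = 30% (8.7% to 60.7%);
- truth if both develop it: 5/10 = 50% (22.2% to 77.8%);
- truth if neither does, for example because both die first: 3/10 = 30%.

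Dropping them understates incidence in one case (37.5% against 50%) and overstates it in the other (37.5% against 30%).

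**The case against.** The strongest reply is that two explicit follow-up rules stand against one phrase. Section 5.4 covers stopping for any reason, and Section 5.5 sets a schedule after treatment ends. Section 5.4 also lists removal from study by the investigator among the reasons that treatment ends, so the protocol uses the two ideas loosely. If sites follow 5.4, no such censoring arises. This stands: the bias is conditional on 5.8 prevailing. It does not remove the contradiction, because 5.8 names leaving the study as a step separate from stopping the drug.

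A reader might also infer that Section 5.5 ends follow-up for these patients once the event settles. The text does not establish that. It does not say that follow-up stops there, and the sentence can be read as an addition to the general schedule. It concerns unacceptable adverse events, which 5.4 lists separately from unresolved acute GvHD.

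The link between this event and later death is plausible, but the documents neither cite nor quantify it. Section 1.1 does not name acute GvHD among its risk factors for chronic GvHD. The link is therefore an assumption here. Patients with fewer than 2 cycles fall outside the secondary-endpoint set whatever 5.8 says, and the primary endpoint is safety in all treated patients to 30 days after the last dose.

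**Conclusion.** The contradiction between 5.8 and Sections 5.4 and 5.5 is real. If 5.8 is applied literally, survival and relapse are censored for a reason that is probably not independent of outcome. In the illustrations with one other death, survival is overstated by 8.9 points (one removed) or 17.5 points (two removed) if all removed patients die, and understated by 1.1 or 2.5 points if none die. These counts are assumed, and no size or direction is claimed for relapse.

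A reader might go further and conclude that the highest-risk patients will be lost and that both survival and chronic GvHD results will look too good. The documents do not support that. The loss depends on which section governs. For chronic GvHD, steroid use and second-line treatment, no censoring rule is stated and death is a competing event, so the direction is open.

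Severity is moderate. This is a descriptive pilot with a safety primary endpoint, but its data are meant to feed phase II sample-size estimates, and follow-up that was never collected cannot be recovered in the analysis.

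**What to change.** - **Reconcile 5.8 with 5.4 and 5.5.** State that a patient who meets this criterion is off study treatment but stays in follow-up for vital status, relapse and GvHD status. Follow-up should end only at death, withdrawal of consent, loss to follow-up, study closure or the planned end of follow-up.
- **Clarify 5.5.** Say that following an adverse event to resolution or stabilization is in addition to the scheduled visits.
- **Reconcile the triggers.** Section 5.4 turns on lack of response to therapy, and 5.8 on failure to reach grade II or lower. The sponsor should settle one wording. This review takes no view on which.
- **State the handling in 8.2 and 13.** For each secondary endpoint, say how patients who leave early enter the estimate and its denominator, and how death before chronic GvHD is counted.

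The cost is a few sentences. Section 12 already provides follow-up, progression and death forms. One detail needs checking: the Section 10.2 calendar starts 6 months after the first dose and has no row for survival or relapse. With the first dose at Day +30 to +80, and taking 6 months as 180 days, the 6-month post-transplant assessment falls 100 to 150 days after the first dose, before that visit. The amendment should therefore say which visits apply to a patient who stops early.

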5.2 Study Drug Administration

Belimumab will be administered intravenously at 10 mg/kg over 1 hour. Enrollment and the first dose of belimumab (Cycle 1) will be administered between Day +30 and Day +80 after alloHCT, after reviewing bone marrow biopsy results and confirming eligibility. Subjects will receive belimumab every 2 weeks for 3 cycles and then every 4 weeks for a total of 7 cycles (6 months of therapy).

Therefore: Cycle 1 of belimumab will be administered between Day +30 and +60 after alloHCT, Cycle 2 will be administered 2 weeks later (+/- 3 days), Cycle 3 will be administered two weeks after Cycle 2 (+/- 3 days), and each subsequent cycle will be given every 4 weeks thereafter (+/- 1 week) for total of 7 cycles (6 months of therapy). This dosing and schedule of belimumab administration is similar to prior phase III studies for systemic lupus erythematosus [38, 39]. Subjects will continue to adjust their standard of care immunosuppressive medications at the discretion of treating physician.

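### Sections 5.8 and 5.4 conflict on follow-up after unresolved grade III-IV acute GvHD; followed literally, 5.8 ends it before the 12- and 24-month landmarks

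*Combined protocol and SAP*

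**What the plan says.** All references are to the combined protocol and SAP.

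- **Section 5.8 (Acute GvHD).** Belimumab is held for grade III-IV acute GvHD that arises after treatment starts. If the grade is not II or less after a delay of up to two weeks, "belimumab will be discontinued indefinitely and patient will be taken off study".
- **Section 5.4 (Duration of Therapy).** The list of reasons to end treatment includes "Grade III-IV acute GvHD not responding to therapy after 2 weeks" and also "Investigator removes the patient from study". The section closes with: "Subjects who prematurely discontinue treatment for any reason will be followed as indicated in the study calendar".
- **Section 5.5 (Duration of Follow-up).** Follow-up after treatment runs every 3 months to 2 years from C1D1, then annually to 5 years or death. The last sentence reads: "Subjects removed from study for unacceptable adverse events will be followed until resolution or stabilization of the adverse event".
- **Section 8.2 (Secondary Endpoints).** "Subjects who receive at least 2 cycles of belimumab are evaluable for secondary and explorative endpoints". The landmarks are 6, 12 and 24 months (3 and 6 months for acute GvHD). Overall survival and relapse use "censoring at last follow up date for those with incomplete observations". No rule is given for incomplete chronic GvHD, steroid or alternative-treatment data.
- **Section 10.2 (Follow-Up Calendar).** Chronic GvHD and immunosuppressive medication are assessed at seven visits, from +6 to +24 months after C1D1.

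**The concern.** For nearly the same clinical event, one section stops the drug and the other stops the drug and also ends study participation. A site managing severe GvHD will probably turn to Section 5.8, the specific rule. If it is followed as written, scheduled follow-up for chronic GvHD, relapse, survival and steroid use ends for subjects whom Section 8.2 still counts as evaluable.

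The loss would not be random. Removal is triggered by severe acute GvHD that has not come under control, which is plausibly related to later chronic GvHD, steroid exposure and death. Censoring survival and relapse at about the time of removal would then be informative. Section 13 intends these data to feed the sample size of a later phase II study, so the direction of any error matters even without a hypothesis test.

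**Working it through.** The plan gives no figure on this point. The check compares the texts and then works out when a literal removal would occur.

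**1. The texts side by side.** The triggers differ slightly: no response to therapy after two weeks (5.4), against no improvement to grade II or less within the hold (5.8). A subject who meets 5.8 has in any case discontinued early, so the closing sentence of 5.4 applies and calls for calendar follow-up. Section 5.8 adds a second instruction that, taken at its word, ends it. Section 5.5 can be read either way: its sentence on adverse events may replace scheduled follow-up or add to it. No section defines off study.

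**2. Latest removal.** Inputs:

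- Schedule (5.2): "Subjects will receive belimumab every 2 weeks for 3 cycles and then every 4 weeks for a total of 7 cycles". Nominal dose days from C1D1 are 0, 14, 28, 56, 84, 112 and 140.
- C1 at day 30 to 80 after alloHCT (5.2; one sentence there says day 60, and 80 gives the later bound).
- Windows (5.2, 10.1): 3 days each for C2 and C3, 7 days each for C4 to C7.
- Hold (5.8): 14 days. The last dose that can be held is C7.
- Month 12 is taken as day 365 and month 24 as day 730.

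Results:

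- Nominal: 140 + 14 = day 154 from C1D1. With C1 at day 80: 154 + 80 = **day 234** after alloHCT.
- Every window used late: 3 + 3 + 4 × 7 = 34 days. 154 + 34 = 188; 188 + 80 = **day 268**.
- Stress case, with a two-week infection hold (5.7) on each of the six later doses: 268 + 6 × 14 = day 352.

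All three fall before day 365. Counting months from C1D1 instead gives the same answer, because 154 and 188 are also below 365.

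**3. Earliest removal with two doses given.** This depends on when the two weeks start. Counted from onset on the day of C2: 14 + 14 + 30 = day 58 after alloHCT. Counted from the next due dose (C3): 28 + 14 + 30 = day 72. The latest date does not depend on this choice in any important way. Section 5.8 does not say which clock applies.

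**4. What is not observed.** From the latest removal to day 730: 730 − 234 = 496 days, or 16.3 months at 30.44 days per month; with all windows used, 730 − 268 = 462 days, or 15.2 months. The first follow-up visit is at week 24 (day 168 from C1D1). At nominal dosing this is after day 154, so all 7 chronic GvHD visits in Section 10.2 are lost. They are part of 12 scheduled assessments in all (C3 to C7 plus 7).

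**5. Effect on a rate.** Section 13 plans a 90% exact binomial interval with N = 10. Suppose, for illustration only, that 5 of 10 would have chronic GvHD by 24 months: 5/10 = 50.0% (90% CI 22.2 to 77.8). If one of the five is removed under 5.8 and develops the disease afterwards, but stays in the denominator: 4/10 = 40.0% (15.0 to 69.6). If the removed subject never develops it, or was diagnosed before removal, the count stays at 5/10.

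**6. How many subjects.** The documents give no rate. Let q be the assumed chance that a subject receives two cycles and then meets the 5.8 rule. The chance of at least one in 10 is 1 − (1 − q)^10: 40% at q = 5%, 65% at 10%, 80% at 15% and 89% at 20%. These rates are assumptions.

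**The case against.** The best answer is that the protocol, read as a whole, already keeps these subjects in follow-up. Section 5.4 applies to discontinuation for any reason. Its list includes removal from study by the investigator and still ends in calendar follow-up, so the protocol uses removal from study loosely. Section 5.5 likewise speaks of subjects removed from study who are then followed. Section 5.8 is a treatment-management section and does not say that follow-up ends. On this view off study means off treatment. This argument is strong, and it limits the point to a conflict of wording whose harm is conditional. It does not remove the conflict, because nothing says which section governs.

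It is also fair that the trial is a descriptive pilot of 10, that the event may never occur, and that a 10-point shift is small beside an interval about 56 points wide (77.8 − 22.2 = 55.6). All of this stands.

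A reader might infer that the primary safety endpoint is compromised too. The documents do not support that. Sections 7, 8.1 and 10.1 call for adverse event collection to 30 days after treatment, with no exception for this event, and Section 5.5 follows adverse events to resolution or stabilization. The safety window is largely protected.

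**Conclusion.** The concern holds as a conflict between current instructions that should be corrected. Sections 5.8 and 5.4 cannot both be followed if off study means what it says. On that literal reading, a subject evaluable under Section 8.2 leaves by day 234 after alloHCT at nominal dosing, or day 268 with every window used. Status at 12 and 24 months is then not observed under the protocol, and survival and relapse are censored near removal for a reason related to outcome.

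The size is limited. The number affected is unknown and may be zero, each subject is 1 of 10, and only secondary and exploratory descriptive endpoints are materially affected.

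Two stronger readings are tempting. A reader might infer that the plan certainly loses these data; it does so only if 5.8 overrides the closing sentence of 5.4. A reader might also infer that such subjects drop out of the denominator, so that a chronic GvHD rate could move up or down. The documents state no such exclusion, and Section 8.2 keeps the subjects evaluable. With N = 10 retained, the risk is an uncounted later case (4/10 instead of 5/10 in the illustration), together with missing later severity and steroid data.

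The dates assume that C7 is the last dose that can be held and that no infection holds intervene. The stress case with six such holds still falls before month 12.

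**What to change.** In Section 5.8, replace the clause that takes the patient off study with: *and the subject will come off study treatment but remain on study, with adverse event collection to 30 days after the last dose and follow-up per Section 10.2*. In Section 5.5, end the last sentence with: *in addition to the scheduled follow-up above*.

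The cost is two wording edits in one amendment. Section 10.2 already schedules the visits, and the criterion for stopping belimumab does not change. If the sponsor always meant off treatment, the edits state that intent; if not, they prevent an outcome-related loss of follow-up.

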5.9 Women of Childbearing Potential

Women of childbearing potential (defined as women with regular menses, women with amenorrhea, women with irregular cycles, women using a contraceptive method that precludes withdrawal bleeding, and women who have had a tubal ligation) are required to have a negative pregnancy test within 7 days prior to the first dose of belimumab.

Women of childbearing potential must agree to one of the following:

- Complete abstinence from intercourse from 2 weeks prior to administration of the first dose of belimumab until 16 weeks after the last dose of belimumab (if consistent with the preferred and usual lifestyle of the patient). Periodic abstinence (e.g., calendar, ovulation, symptothermal, post-ovulation methods) and withdrawal are not acceptable methods of contraception.
- Consistent and correct use of one of the following acceptable methods of birth control for one month prior to the start of the study agent, during the study, and 16 weeks after the last dose of study agent:
 - Oral contraceptive, either combined or progestogen alone
 - Injectable progestogen
 - Implants of levonorgestrel or etonogestrel
 - Estrogenic vaginal ring
 - Percutaneous contraceptive patches
 - Intrauterine device (IUD) or intrauterine system (IUS) with < 1% failure rate as stated in the product label
- Male partner sterilization (vasectomy with documentation of azoospermia) prior to the female subject's entry into the study, and this male is the sole partner for that subject. For this definition, "documented" refers to the outcome of the investigator's/designee's medical examination of the subject or review of the subject's medical history for study eligibility, as obtained via a verbal interview with the subject or from the subject's medical records.
- Double barrier method: condom and occlusive cap (diaphragm or cervical/vault caps) plus spermicidal agent (foam/gel/film/cream/suppository)

If a patient is suspected to be pregnant, belimumab should be immediately discontinued. In addition, a positive urine test must be confirmed by a serum pregnancy test. If it is confirmed that the patient is not pregnant, the patient may resume dosing. If a female

patient or female partner of a male patient becomes pregnant during therapy or within one month after the last dose of belimumab, the investigator must be notified in order to facilitate outcome follow-up.

